10.0 Setting

10.1 The baseline assessment and 12-week follow-up assessment components of the research will take place at the University of Houston College of Nursing Campus at [name]. The Community-based Intervention group Qigong classes will take place at [name]. Classes will be held every Wednesday at 2pm.

11.0 Risks to Subjects

11.1 There is a potential for minor musculoskeletal aches and pain that might result due to the Qigong exercises in both the community-based and internet-based programs. These are typical in any low intensity physical activity program. Participants will be instructed and regularly reminded to adjust the level of activity based on their individual abilities. Nonetheless, our instructors are BLS-trained, and [name] will be available by phone in the event of an adverse event. All participants who participate in the study will have the opportunity to withdraw at any time. There are no other known or anticipated risks of physical, mental or social injury to those who will participate in the study.

11.2 When starting an exercise program, individuals may experience temporary muscle soreness or stiffness. Increased physical activity may worsen an underlying pain condition. These unlikely but possible conditions will be monitored closely at each testing visit. If, at any point, an issue is detected, participants will be immediately referred back to their primary provider for routine care.

11.3 We will utilize a multi-pronged approach to monitor safety and track Adverse Events (AEs) throughout the study with formal oversight by a University of Houston, Institutional Review Board. For participants attending community classes, instructors will be trained to track and report any observed or participant-reported AE in an AE log provided by the study. Participants assigned to both community- and internet-based training will also be asked to complete an AE survey as part of the home practice log, which are sent to study staff weekly. Participants in the self-care control group will be called monthly to ask about any adverse events, and more generally, to maintain contact with study staff. Finally, all participants will be queried in person at 12 weeks about AEs experienced over the course of the study. When an adverse event is reported through any of the above tracking mechanisms, the study PI will be

FULL PROTOCOL TITLE: CARING FOR CAREGIVERS WITH MIND-BODY EXERCISE

notified. Any adverse events experienced are followed by the PI and reported to the University of Houston IRB according to established guidelines. If the participants have any questions about their rights as a subject or how this research study is being conducted, they are told in the written consent form to contact [name].

12.0 Potential Benefits to Subjects

- 12.1 CGs represent a well-defined, large and growing subset of a larger population of CGs that overlap greatly in the constellations of morbidities that lead to high levels of distress. The multi-modal nature of the Eight Brocades Qigong regimen explicitly targets both psychosocial and physical functional symptoms, thus expanding the scope of mind-body studies for CGs to date, which have largely focused on stress management and psychological wellbeing.
- 12.2 Our pilot study, and our eventual large-scale comparative effectiveness trial, explores the effectiveness of Qigong training delivered in both community-based group classes and through self-guided internet-based modules supplemented with one-on-one virtual learning support. This design is innovative for multiple reasons. A finding that both methods are effective would lead to multiple options for CGs. Those with flexible schedules and seeking group support and the opportunity for a change of environments might choose community classes. Those with unpredictable and inflexible schedules and an inability to leave the home could develop a self-guided training plan, with one-on-one virtual support scheduled at a convenient time. More generally, the evidence-base for DVD- and internet-based learning of mind-body exercise is essentially non-existent. Studies are desperately needed to evaluate whether the promising evidence of Qigong's effectiveness based on group and instructor lead clinical trials is also observed when instructions are delivered virtually.
- 12.3 Since risks of the study are minimal, and the benefits are potentially large, the risk-benefit ratio is strongly on the side of benefit.

13.0 Withdrawal of Subjects

- 13.1 All participants who participate in the study will have the opportunity to withdraw at any time.

14.0 Costs/Payments to Subjects

- 14.1 The study intervention and all related items (parking costs, iPads, tablets, caregiver helpbook, etc.) will be provided at no cost to participants. Participants will be compensated for participating in the study with \$125 in Amazon gift cards. A \$50 gift card will be provided after the baseline assessment, another \$50 gift card will be provided after the 12-week follow up assessment, and a final \$25 gift card will be provided after the completion of the 6-month follow-up survey.

15.0 Confidentiality

FULL PROTOCOL TITLE: CARING FOR CAREGIVERS WITH MIND-BODY EXERCISE

- 15.1 Participant confidentiality will be maintained at all times. Each participant will be given a unique study ID that does not contain personal identifying information and will be used for all research purposes. Names, code numbers and telephone numbers will be kept in locked secure files, separate from the study data. Likewise all physical study data will be kept in locked storage and all electronic study data will be password protected with access restricted to approved personnel. Any document linking the participant name to an identification number will be kept in a locked file separate from data collection files. Study reports will be aggregated so that individual participants are not identified. All data will be stored in databases, identified only by study ID number, behind appropriate firewalls and with institutional backup.
- 15.2 Only the Principal Investigators and grant coordinator will have access to the names associated with the identifiers, which will be kept locked in separate files.
- 15.3 Hard copies of identifiable data will be shredded within 5 years from the completion of the study date (08/31/2026) or by the time all data has been published in manuscript format, whichever comes first.
- 15.4 Electronic identifiable data will be physically destroyed by the services provided by the Iron Mountain Information Management which is AAA certified by the National Association for Information Destruction.
- 15.5 Recordings will be destroyed after transcription of audiotapes.

16.0 Provisions to Protect the Privacy Interests of Subjects

- 16.1 Participants will be assured that personal identifiers will be detached from all data and a random study ID number will be used. Only the PI and research assistant will have access to the study ID code. In-person assessments will be held in a private room. Phone calls concerning the study will be prefaced by the research team asking if the participant is comfortable discussing their study activities at that time, and if they are not, an alternate phone call time will be established.
- 16.2 At any point that a participant feels uncomfortable with questions or study procedures, we will remind the participant that it is a voluntary study and they do not have to proceed.

17.0 Informed Consent Process

- 17.1 Informed consent will be obtained from all participants. The consent process will take place upon the participant's arrival for the baseline assessment, prior to any study procedures. The consent form will describe the purpose of the

FULL PROTOCOL TITLE: CARING FOR CAREGIVERS WITH MIND-BODY EXERCISE

study, the procedures to be followed, and the risks and benefits of participation. Each page of the consent form will be reviewed with the participant prior to their signing. Approximately 20-30 minutes will be devoted to discussing the consent form, and the participant will have unlimited time to ask any questions. After the consent form has been discussed, a signed copy of the consent form will be obtained from each participant. A copy will also be given to each participant and this fact will be documented in the participant's record. This research will be following "SOP: Informed Consent Process for Research (HRP-090)." Participants who are unable to provide informed consent are ineligible from study participation.

Interested participants will be pre-screened for eligibility over the phone. A waiver of written documentation of consent for prescreening has been requested.

a. The written script of the information to be provided orally can be found within the Phone Screen Template (attached). The written script of the information to be provided and all written information to be provided include all required and appropriate additional elements of consent disclosure.

b. The research presents no more than Minimal Risk of harm to subjects.

- Qigong is considered a low, impact mind-body exercise program. Stretching will be completed prior to the initiation of our program. Participants will be encouraged to practice at their own pace, and take rests according to their needs. In addition, subjects will be regularly monitored for adverse effects of exercise during visits. Subjects in the community-based and internet-based programs will be instructed to notify their healthcare provider first, and then study staff of any changes in health status. The PI will contact participants by telephone if any reported adverse event suggests clinical deterioration warranting immediate medical attention. During the study, if a subject experiences a medical problem as deemed by the study physician or subject's regular care provider that prevents participation in the Qigong program, he/she will be temporarily suspended from the study and will resume when at baseline clinical status.*

c. The research involves no procedures for which written consent is normally required outside of the research context.

- The research does not involve any procedure for which additional consent is required. All components of the research have been addressed within the consent.*

d. Written information describing the research is to be provided to the subject, or the subject's legally authorized, representative.

- This includes the detailed consent form, flyer, and a specific letter addressed to participants based on their randomization to either the community-based, internet-based, or self-care group.*

FULL PROTOCOL TITLE: CARING FOR CAREGIVERS WITH MIND-BODY EXERCISE

17.2 *Non-English Speaking Subjects*

Not applicable.

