7.0 Study Timelines

7.1 For Cohorts 1 and 2, we will randomize (1:1:1) 24 CCGs to one of three conditions: (1) A community- based Qigong program; (2) an internet-based Qigong program; or (3) a self-care control group. For Cohort 3, we will randomize (2:1) 15 CCGs to one of two conditions: (1) an internet-based Qigong Program, or (2) a self-care control group. For Cohort 4, we will randomize (2:1) 15 CCGs to one of two conditions: (1) a community-based Qigong program, or (2) a self-care control group. Our primary outcomes are feasibility and acceptability.

7.2 Participants in the community-based programs will attend one, 75 minutes class per week supplemented by home practice (guided by printed materials) for 20 minutes on 3 additional days. Participants in the internet-guided program will be asked to follow two online sessions for 40 minutes each, also supplemented by home practice for 20 minutes on 3 additional days. Participants in both Qigong groups will commence training within 2 weeks of baseline visits. Caregivers randomized to either Qigong intervention can expect a total time commitment of 30 hours to complete all study related activities.

Individuals randomized to the self-care control group will be provided with an educational book on caregiving, they will also be provided with a “Self-Care Manual” that includes self-guided activities related to caregiving and caregiver health. Caregivers randomized to this group can expect about a 5-hour total time commitment to study related activities.

7.3 Baseline and 12-week assessments including psychosocial measures and QOL, physical function and cognitive measures will occur in person for all participants at the University of Houston College of Nursing in Sugarland, [name]. In addition, a short qualitative interview will be conducted with participants in the community-based and internet-based classes. A longer-term 6-month follow-up will assess psychosocial and QOL measures using a mail-in questionnaire packet. Primary analyses should be complete by 08/31/2021.

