At the initial visit at University of Houston, College of Nursing, participants will complete informed consent. This date will be recorded on a case report form as the date of enrollment into the study.

In addition, at this visit initial assessment related to QOL, psychological well-being, caregiver burden, cognitive and physical function will be measured. All outcomes will be assessed at baseline and 12 weeks, following completion of the 12-week intervention. All in-person assessments will be conducted by trained research assistants. Baseline and follow-up assessments are estimated to require 2.0 hours.

At the baseline and 12-week appointments, consented participants will be videotaped performing the Eight Brocades. This video will help assess learnability of the intervention and help with the development of the scoring instrument.

Semi-structured, open-ended interviews lasting approximately 30 minutes will be conducted at the 12-week assessment for participants in all groups. Questions will focus on characterizing participants' perceived effectiveness and enjoyability of the Qigong intervention, both community-based and internet-based, and identifying facilitators and barriers to participation. Questions specific to the mode of intervention delivery may include those related to use of technology, the role of face-to-face instructor feedback, perceived motivators to adherence, and self-efficacy.

In weeks 1, 2, 4 and 6 of the program, participants will participate in a one-to-one call with a Qigong instructor. This call will be audio recorded and will give participants

FULL PROTOCOL TITLE: CARING FOR CAREGIVERS WITH MIND-BODY EXERCISE

the opportunity to address any training- related questions or concerns, and to receive personalized feedback and encouragement from the instructor. At the 12-week assessment, participants will be asked to return the computer tablet. Participants will

FULL PROTOCOL TITLE: CARING FOR CAREGIVERS WITH MIND-BODY EXERCISE

be asked to keep track of their home Qigong practice on provided logs throughout the study. We will ask participants to send their logs to the study researchers at the end of each week, and we will provide them with stamped envelopes for mailing.

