- **Timed Up-and-Go Single and Dual Task** will be completed among participants. For the single task, CGs will be asked to sit in a chair with their back against the back of the chair. When the researcher says, “Go,” the participant will walk briskly around a marker on the floor and back to the chair. The stopwatch is stopped when the participant’s backside and back are against the chair. For the dual task, the participant completes the steps above in addition to counting backwards by 3s from 100. Both tests will involve two trials.
- **Digit Span**⁴⁵ measures verbal short-term memory. Participants will be asked to repeat numbers in a specific order. Performance is indicated by the average number of digits correctly remembered.
- **Trail Making Test** Parts A & B⁴⁶ consist of 25 circles distributed over a sheet of paper. Participants are timed as they connect the circles without lifting the pen or pencil from the paper.

The following is a table of study measures:

Measure	Description
QOL	
 • Promis-29. 29 items consisting of self-reported health measures in the domains of physical health, mental health and social health.
Depression	
 • Patient Health Questionnaire-9 (PHQ-9). 9 items measuring depression and used to grade severity of symptoms.
Anxiety	
 • Generalized Anxiety Disorder (GAD-7). 7 item tool used for screening, diagnosis and severity assessment of anxiety disorder.
Fatigue	
 • Brief Fatigue Inventory (BFI): 9 items measuring the severity of fatigue and the impact of fatigue on daily functioning in the past 24 hours.
Perceived Social Support	
 • Multidimensional Scale of Perceived Social Support (MSPSS). 12 item scale designed to measure perceived social support from three sources; Family, Friends and a Significant Other.
Sleep Disturbances	
 • Pittsburgh Sleep Quality Index (PSQI): 19 items measuring patients’ sleep quality, sleep latency, sleep duration, habitual sleep efficiency, sleep disturbances, sleeping medication use, and daytime dysfunction over the past month.
Perceived Stress	
 • Perceived Stress Scale (PSS). 10 item psychological instrument measuring the perception of stress.

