18.0 Process to Document Consent in Writing

18.1 This study will be following “SOP: Written Documentation of Consent (HRP-091).”

19.0 Data Management

19.1 Data will be managed using the REDCap data management system supported through UH. REDCap is a secure, web-based application for managing online databases. REDCap provides automated export procedures for seamless data downloads to Excel and common statistical packages such as SAS. Case report forms will be produced using built-in features of REDCap.

Feasibility. We will use descriptive statistics to evaluate recruitment and retention rates, attendance at classes, and adherence with online intervention. Retention rate will be reported by group at the end of the study. Attendance will be recorded as the proportion of classes attended for community-based classes; and online video tutorial use, logs of home practice, numbers of logins to the webpage, clicks on education links, downloads and views of videos for the internet-based classes. We will consider study retention successful if the retention rate is at least 80% at 12 weeks, and attendance at in-person classes and home compliance to internet-based lessons is at least 70%. Similar criteria will be set for internet-based compliance as well as home practice compliance in both groups. We will test for non-inferiority of the observed rates relative to the expected rates of retention and attendance assuming that the retention and attendance rates follow a beta-binomial distribution. Non-inferiority margins will be determined as 90% lower confidence bounds on the estimated rate for participants in each group. Maximum likelihood will be used to obtain significance and confidence intervals. Relative risk of non-completion between each Qigong training method and self-care control group will be used to represent study completion rates with inference based on separate Fisher’s exact tests.

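### Section 17.1b suspends a medically unwell Qigong participant from the study rather than from Qigong; taken literally, this conflicts with the 12-week assessments and adverse event query required for everyone

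*Combined protocol and SAP*

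**What the plan says.** Section 17.1, item b, deals with a medical problem, as judged by the study physician or the participant's own care provider, "that prevents participation in the Qigong program". The consequence is that "he/she will be temporarily suspended from the study and will resume when at baseline clinical status". The only end point is clinical recovery. Nothing covers recovery after week 12, or no recovery.

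Other sections set follow-up without exceptions:

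- Section 7.3 places the baseline and 12-week assessments in person for every participant, and adds a 6-month stage: "A longer-term 6-month follow-up will assess psychosocial and QOL measures using a mail-in questionnaire packet".
- Section 9.2: "All outcomes will be assessed at baseline and 12 weeks, following completion of the 12-week intervention".
- Section 11.3: "all participants will be queried in person at 12 weeks about AEs experienced over the course of the study".
- Section 19.1 sets the feasibility target: "We will consider study retention successful if the retention rate is at least 80% at 12 weeks".

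Section 13.1 covers voluntary withdrawal only. It does not address follow-up after the intervention is paused.

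**The concern.** The trigger concerns fitness for Qigong, but the consequence reaches the whole study. Controls receive a book and a self-care manual, so a control with the same illness cannot meet the trigger and stays in follow-up. If staff apply the sentence as written, 12-week data could be late or missing because of ill health in the two Qigong arms and not in control.

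Three planned analyses in section 19.1 use that visit or completion of it:

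- 12-week retention, reported by group against 80%.
- The relative risk of non-completion, each Qigong arm against control, tested by Fisher's exact test.
- The 12-week treatment-by-visit contrast, used to help choose outcomes for the future trial.

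Feasibility is a primary outcome (section 7.1), so retention is a main result of this pilot.

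Adverse event ascertainment is also left unclear. In the Qigong arms the weekly adverse event survey forms part of the home practice log (section 11.3). The plan does not say whether someone who has stopped practising still returns it.

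**Working it through.** **Do the sections conflict?** Take a Qigong participant with a qualifying medical problem.

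1. *Recovered before week 12.* The suspension is over by the visit, so there is no conflict at week 12 on either reading.
2. *Not recovered, and suspension means Qigong only.* Sections 7.3, 9.2 and 11.3 apply unchanged. No conflict.
3. *Not recovered, and suspension means the study.* The person is outside the study when those three sections require an in-person assessment and adverse event query. Both instructions cannot be followed: the visit is delayed or missed. The documents give no visit window that would settle which.

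The conflict therefore needs both non-recovery by week 12 and a literal reading. No other section says that assessments continue during a suspension, that the visit moves, or how a suspended person counts toward retention.

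**Which 12-week elements need fitness for Qigong?** The video does: "At the baseline and 12-week appointments, consented participants will be videotaped performing the Eight Brocades". The Timed Up-and-Go needs some physical capacity: "the participant will walk briskly around a marker on the floor and back to the chair". Grip strength is also a physical test. The questionnaires, Digit Span, Trail Making Test and adverse event query do not require Qigong, and the 6-month packet is mailed.

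**What does one lost participant cost?** The plan gives no suspension rate and no figure of its own on this point, so only a unit cost can be shown.

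- Expected arm sizes from section 7.1: community 8 + 10 = 18; internet 8 + 10 = 18; control 8 + 5 + 5 = 18; total 54.
- One loss: 1/18 = 5.6 percentage points of an arm's retention; 1/54 = 1.9 points overall.
- 80% within an arm: 0.80 × 18 = 14.4, so 15 must be retained and at most 3 lost (15/18 = 83.3%; 14/18 = 77.8%).
- 80% overall: 0.80 × 54 = 43.2, so 44 must be retained and at most 10 lost (44/54 = 81.5%; 43/54 = 79.6%).

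The plan reports retention by group but does not say at which level the 80% applies, so both are given. These are the costs of losing any participant for any reason. They show how little room the target leaves and do not estimate the effect of the suspension rule.

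**The case against.** The case on the other side is substantial. The sentence sits in the consent section, where it supports the minimal-risk statement behind a waiver of written consent for prescreening. Staff scheduling visits would more naturally work from sections 7.3, 9.2 and 11.3, which are explicit and cover everyone. The sentence says the suspension is temporary and that the person resumes, and it cancels no visit, questionnaire or query. Section 17.1b has participants tell study staff about changes in health, and section 11.3 has the investigator follow adverse events, so contact during illness is expected. The planned mixed model keeps participants with incomplete visits. Finally, someone too ill for gentle, self-paced exercise may be unable to attend a two-hour in-person visit whatever the wording.

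Most of this stands and limits the severity. It makes a Qigong-only pause the likelier intention and a delayed visit as plausible as a missed one. The last argument also shows that rewording alone would not recover every assessment, so the fix needs a remote option.

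It does not remove the contradiction. This is the only rule for a medically unfit participant, and no section says it yields to the others. The mixed model does not remove bias if data are missing because of unmeasured health status.

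A reader might infer that the plan deliberately drops unwell Qigong participants from follow-up, or that the rule is a demonstrated source of bias. The documents support neither. A reader might also treat the missing time limit as a separate fault. A clinical end point is stated, and the open duration matters here only if assessments are suspended along with Qigong.

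**Conclusion.** The point holds as a low-severity correction. As worded, section 17.1b can apply only in the Qigong arms and, for anyone not recovered by week 12, conflicts with follow-up that the plan requires of all participants. The possible result is late or missing 12-week data, for health reasons, in those arms alone.

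Harm requires a medical problem that prevents Qigong, no recovery by week 12, and staff who take the suspension to include assessments. Data are lost, rather than late, only if no assessment follows on resumption. With no suspension rate in the documents, the effect cannot be estimated: it is probably small and may be zero. The case for acting is that the wording is wrong on its face for what was probably intended and is cheap to correct.

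**What to change.** In section 17.1b, change what is suspended. Suggested wording: *suspended from Qigong classes and home practice; adverse event follow-up and the 12-week and 6-month assessments continue as scheduled*. Add two provisions:

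- The Eight Brocades video and the physical-function tests (Timed Up-and-Go, grip strength) are omitted if the study physician or regular care provider judges them unsafe.
- The questionnaires and adverse event query are taken by mail or phone if the person cannot attend.

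The clinical criteria for pausing and resuming Qigong stay as they are. Once assessments no longer depend on the suspension, its length does not affect follow-up, so no time limit is needed for this purpose.

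The cost is a short edit and no added visits. The downsides are occasional adverse event calls, some missing video and physical-test values, and a few questionnaires collected remotely. Cognitive tests would still be lost for anyone unable to attend in person.
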